11.6 Data Management and Monitoring/Auditing

This study will be conducted in compliance with the Data Safety Monitoring Plan (DSMP) of the Robert H. Lurie Comprehensive Cancer Center of Northwestern University (please refer to NOTIS for additional information). The level of risk attributed to this study requires high monitoring, as outlined in the [DSMP](#). The assigned QAM, with oversight from the Data Monitoring Committee, will monitor this study in accordance with the study phase and risk level.

This study will be conducted in compliance with the Data Safety Monitoring Plan (DSMP) of the Robert H. Lurie Comprehensive Cancer Center of Northwestern University (please refer to NOTIS for additional information). The level of risk attributed to this study requires High Intensity Monitoring as outlined in the DSMP. The assigned QAM, with oversight from the Data Monitoring Committee, will monitor this study in accordance with the study phase and risk level.

Once a subject is confirmed and registered to the study, eCRFs should be submitted according to the detailed data submission guidelines (provided in a separate document).

11.7 Adherence to the Protocol

Except for an emergency situation in which proper care for the protection, safety, and well-being of the study patient requires alternative treatment, the study shall be conducted exactly as described in the approved protocol.

11.6.1 Emergency Modifications

Investigators may implement a deviation from, or a change of, the protocol to eliminate an immediate hazard(s) to trial subjects without prior IRB approval.

For any such emergency modification implemented, an IRB modification form must be completed within 5 business days of making the change, and the QAM must be notified within 24 hours of such change.

11.6.2 Other Protocol Deviations

All other deviations from the protocol must be reported to the assigned QAM using the appropriate form.

A protocol deviation is any unplanned variance from an IRB approved protocol that:

- Is generally noted or recognized after it occurs.
- Has no substantive effect on the risks to research participants.
- Has no substantive effect on the scientific integrity of the research plan or the value of the data collected.
- Did not result from willful or knowing misconduct on the part of the investigator(s).

A protocol deviation may be considered an instance of Reportable New Information (RNI) if it:

NU Study Number: NU 16N03
BMS Study Number: CA 209-802

- Has harmed or increased the risk of harm to one or more research participants.
- Has damaged the scientific integrity of the data collected for the study.
- Results from willful or knowing misconduct on the part of the investigator(s).
- Demonstrates serious or continuing noncompliance with federal regulations, State laws, or University policies.

11.8 Investigator Obligations

The Principal Investigator is responsible for the conduct of the clinical trial at the site in accordance with Title 21 of the Code of Federal Regulations and/or the Declaration of Helsinki. The PI is responsible for personally overseeing the treatment of all study patients. The PI must assure that all study site personnel, including sub-investigators and other study staff members, adhere to the study protocol and all FDA/GCP/NCI regulations and guidelines regarding clinical trials both during and after study completion.

The Principal Investigator at each institution or site will be responsible for assuring that all the required data will be collected, entered onto the appropriate eCRFs, and submitted within the study-specific timeframes. Periodically, monitoring visits may be conducted and the Principal Investigator will provide access to his/her original records to permit verification of proper entry of data. The study may also be subject to routine audits by the Audit Committee, as outlined in the DSMP.

11.9 Publication Policy

This section should be removed if the trial is not rated as a high intensity trial. All potential publications and/or data for potential publications (e.g. manuscripts, articles, data, text, diagrams, abstracts, posters, charts, slides, pictures, or clinicaltrials.gov releases) must be approved in accordance with the policies and processes set forth in the Lurie Cancer Center DSMP. For trials that require high intensity monitoring, the assigned QAM will prepare a preliminary data summary (to be approved by the DSMC) no later than 3 months after the study reaches its primary completion date (the date that the final subject is examined or receives an intervention for the purposes of final data collection for the primary endpoint). If the investigator's wish to obtain DSMC-approved data prior to this point (or prior to the point dictated by study design), the PI must send a written request for data to the QAM which includes justification. If the request is approved, data will be provided no later than 4 weeks after this request approval. The data will be presented to the DSMC at their next available meeting, and a final, DSMC-approved dataset will be released along with any DSMC decisions regarding publication. The investigators are expected to use only DSMC-approved data in future publications. The investigators should submit a copy of the manuscript to the biostatistician to confirm that the DSMC-approved data are used appropriately. Once the biostatistician gives final approval, the manuscript may be submitted to external publishers.

NU shall provide BMS with a copy of each Publication at the earliest practicable time, but in any event not less than thirty (30) days prior to its submission to a journal, publisher or meeting or fifteen (15) days prior to any public disclosure of any manuscript or other public disclosure (e.g., presentations). To the extent applicable, BMS personnel shall be acknowledged (including authorship where applicable) in accordance with customary scientific practice.

REFERENCES

Appendix A.

Common Terminology Criteria for Adverse Events V4.0.3 (CTCAE)

The descriptions and grading scales found in the revised NCI Common Terminology Criteria for Adverse Events (CTCAE) version 4.0.3 will be utilized for adverse event reporting. (<http://ctep.cancer.gov/reporting/ctc.html>)

Appendix B – ECOG Performance Status

The Eastern Cooperative Oncology Group (ECOG) performance status scale	
Grade	Description
0	Normal activity. Fully active, able to carry on all pre-disease performance without restriction.
1	Symptoms, but ambulatory. Restricted in physically strenuous activity, but ambulatory and able to carry out work of a light or sedentary nature (e.g., light housework, office work).
2	In bed <50% of the time. Ambulatory and capable of all self-care, but unable to carry out any work activities. Up and about more than 50% of waking hours.
3	In bed >50% of the time. Capable of only limited self-care, confined to bed or chair more than 50% of waking hours.
4	100% bedridden. Completely disabled. Cannot carry on any self-care. Totally confined to bed or chair.
5	Dead.

* As published in Am. J. Clin. Oncol.: Oken, M.M., Creech, R.H., Tormey, D.C., Horton, J., Davis, T.E., McFadden, E.T., Carbone, P.P.: *Toxicity And Response Criteria Of The Eastern Cooperative Oncology Group*. Am J Clin Oncol 5:649-655, 1982. The Eastern Cooperative Oncology Group, Robert Comis M.D., Group Chair.

Appendix C – Contraception Requirements

Investigators shall counsel FOCBP and male subjects who are sexually active with FOCBP on the importance of pregnancy prevention and the implications of an unexpected pregnancy. Investigators shall advise FOCBP and male subjects who are sexually active with FOCBP on the use of highly effective methods of contraception from the time of treatment initiation to 5 months (for FOCBP) or 7 months (for males with FOCBP partners) after the last dose of nivolumab. Highly effective methods of contraception have a failure rate of < 1% per year when used consistently and correctly.

At a minimum, subjects must agree to the use of two methods of contraception, with one method being highly effective and the other method being either highly effective or less effective as listed below:

HIGHLY EFFECTIVE METHODS OF CONTRACEPTION

- a) Male condoms with spermicide
- b) Hormonal methods of contraception including combined oral contraceptive pills, vaginal ring, injectables, implants, and intrauterine devices (IUDs) such as Mirena® by FOCBP subject or male subject's FOCBP partner. Female partners of male subjects participating in the study may use hormone based contraceptives as one of the acceptable methods of contraception since they will not be receiving study drug.
- c) Nonhormonal IUDs, such as ParaGard®
- d) Tubal ligation
- e) Vasectomy.
- f) Complete Abstinence*

*Complete abstinence is defined as complete avoidance of heterosexual intercourse and is an acceptable form of contraception for all study drugs. Subjects who choose complete abstinence are not required to use a second method of contraception, but female subjects must continue to have pregnancy tests. Acceptable alternate methods of highly effective contraception must be discussed in the event that the subject chooses to forego complete abstinence.

LESS EFFECTIVE METHODS OF CONTRACEPTION

- a) Diaphragm with spermicide
- b) Cervical cap with spermicide
- c) Vaginal sponge
- d) Male Condom without spermicide*
- e) Progestin only pills by FOCBP subject or male subject's FOCBP partner
- f) Female Condom*

[figure not shown]
*A male and female condom must not be used together

Appendix D- Adverse Event Algorithms

Recommended management algorithms for suspected nivolumab related endocrinopathy, gastrointestinal toxicity, hepatotoxicity, neurologic toxicity, pulmonary toxicity, renal toxicity and skin toxicity

Endocrinopathy Management Algorithm

[figure not shown]
Rule out non-inflammatory causes. If non-inflammatory cause, treat accordingly and continue I-O therapy. Consider visual field testing, endocrinology consultation, and imaging.

Patients on IV steroids may be switched to an equivalent dose of oral corticosteroids (e.g. prednisone) at start of tapering or earlier, once sustained clinical improvement is observed. Lower bioavailability of oral corticosteroids should be taken into account when switching to the equivalent dose of oral corticosteroids.

GI Adverse Event Management Algorithm

[figure not shown]
Rule out non-inflammatory causes. If non-inflammatory cause is identified, treat accordingly and continue I-O therapy. Opiates/narcotics may mask symptoms of perforation. Infliximab should not be used in cases of perforation or sepsis.

Patients on IV steroids may be switched to an equivalent dose of oral corticosteroids (e.g. prednisone) at start of tapering or earlier, once sustained clinical improvement is observed. Lower bioavailability of oral corticosteroids should be taken into account when switching to the equivalent dose of oral corticosteroids.

Hepatic Adverse Event Management Algorithm

Rule out non-inflammatory causes. If non-inflammatory cause, treat accordingly and continue I-O therapy. Consider imaging for obstruction.

[figure not shown]
Patients on IV steroids may be switched to an equivalent dose of oral corticosteroids (e.g. prednisone) at start of tapering or earlier, once sustained clinical improvement is observed. Lower bioavailability of oral corticosteroids should be taken into account when switching to the equivalent dose of oral corticosteroids.

*I-O therapy may be delayed rather than discontinued if AST/ALT ≤ 8 x ULN or T.bili ≤ 5 x ULN.

**The recommended starting dose for grade 4 hepatitis is 2 mg/kg/day methylprednisolone IV.

Neurological Adverse Event Management Algorithm

[figure not shown]
Rule out non-inflammatory causes. If non-inflammatory cause, treat accordingly and continue I-O therapy.

Patients on IV steroids may be switched to an equivalent dose of oral corticosteroids (e.g. prednisone) at start of tapering or earlier, once sustained clinical improvement is observed. Lower bioavailability of oral corticosteroids should be taken into account when switching to the equivalent dose of oral corticosteroids.

Pulmonary Adverse Event Management Algorithm

[figure not shown]
Rule out non-inflammatory causes. If non-inflammatory cause, treat accordingly and continue I-O therapy. Evaluate with imaging and pulmonary consultation.

Patients on IV steroids may be switched to an equivalent dose of oral corticosteroids (e.g. prednisone) at start of tapering or earlier, once sustained clinical improvement is observed. Lower bioavailability of oral corticosteroids should be taken into account when switching to the equivalent dose of oral corticosteroids.

Renal Adverse Event Management Algorithm

[figure not shown]
Rule out non-inflammatory causes. If non-inflammatory cause, treat accordingly and continue I-O therapy

Patients on IV steroids may be switched to an equivalent dose of oral corticosteroids (e.g. prednisone) at start of tapering or earlier, once sustained clinical improvement is observed. Lower bioavailability of oral corticosteroids should be taken into account when switching to the equivalent dose of oral corticosteroids.

Skin Adverse Event Management Algorithm

Rule out non-inflammatory causes. If non-inflammatory cause, treat accordingly and continue I-O therapy.

Patients on IV steroids may be switched to an equivalent dose of oral corticosteroids (e.g. prednisone) at start of tapering or earlier, once sustained clinical improvement is observed. Lower bioavailability of oral corticosteroids should be taken into account when switching to the equivalent dose of oral corticosteroids.

*Refer to NCI CTCAE v4 for term-specific grading criteria.

**If SJS/TEN is suspected, withhold I-O therapy and refer patient for specialized care for assessment and treatment. If SJS or TEN is diagnosed, permanently discontinue I-O therapy.

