4.3.1 Dose delays: Ipilimumab and/or nivolumab

Ipilimumab and/or nivolumab administration should be delayed for the following until resolution to \leq Grade 1 or baseline:

- Any Grade 2 non-skin, drug-related adverse event, except for fatigue and laboratory abnormalities
- Any Grade \geq 3 skin drug-related AE
- Any Grade \geq 3 drug-related laboratory abnormality with the following exceptions for lymphopenia, AST, ALT, or total bilirubin or asymptomatic amylase or lipase:
 - Grade 3 lymphopenia does not require a dose delay
 - If a participant has a baseline AST, ALT, or total bilirubin that is within normal limits, delay dosing for drug-related Grade 2 toxicity
 - If a participant has baseline AST, ALT, or total bilirubin within the Grade 1 toxicity range, delay dosing for drug-related Grade \geq 3 toxicity
 - Any Grade \geq 3 drug-related amylase or lipase abnormality that is not associated with symptoms or clinical manifestations of pancreatitis does not require dose delay.
- Any AE, laboratory abnormality or inter-current illness which, in the judgment of the investigator, warrants delaying the dose of study medication.

Participants that have drug-related toxicities that meet the criteria for dose delay, should have both drugs (ipilimumab and nivolumab) delayed until retreatment criteria are met. (Exceptions apply to the retreatment criteria after dose delay of ipilimumab and nivolumab for Grade \geq 3 amylase and lipase abnormalities that are not associated with symptoms or clinical manifestations of pancreatitis and that are attributed to ipilimumab alone.)

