4.3.2 Treatment discontinuation: Ipilimumab and/or nivolumab

Should the treating physician decide to discontinue treatment given suspicion for a drug-related side effect, the side effect should be attributed to one study drug to the best of the physician's ability. Either ipilimumab or nivolumab should be discontinued based on this attribution, or both if a definite attribution is not possible.

Ipilimumab and/or nivolumab should be discontinued permanently for the following:

- Any Grade 2 drug-related uveitis, eye pain, or blurred vision that does not respond to topical therapy and does not improve to Grade 1 severity within the re-treatment period OR requires systemic treatment
- Any Grade 3 non-skin, drug-related adverse event lasting > 7 days, with the following exceptions for laboratory abnormalities, drug-related uveitis, pneumonitis, bronchospasm, hypersensitivity reactions, infusion reactions, and endocrinopathies:
 - Grade 3 drug-related uveitis, pneumonitis, bronchospasm, hypersensitivity reaction, or infusion reaction **of any duration** (can be < 7 days) requires discontinuation
 - Grade 3 drug endocrinopathies adequately controlled with only physiologic hormone replacement do not require discontinuation
 - Grade 3 drug-related laboratory abnormalities do not require treatment discontinuation except:
 - Grade 3 drug-related thrombocytopenia > 7 days or associated with bleeding (aside from minor bleeds \leq Grade 1) requires discontinuation

NU Study Number: NU 16N03
BMS Study Number: CA 209-802

- Any drug-related liver function test (LFT) abnormality that meets the following criteria require discontinuation:
 - AST or ALT > 5-10 x ULN for > 2 weeks
 - AST or ALT > 10 xUL
 - Total bilirubin > 5 x ULN
 - Concurrent AST or ALT > 3 xULN and total bilirubin > 2 x ULN
- Any Grade 4 drug-related adverse event or laboratory abnormality, except for the following events which do not require discontinuation:
 - Grade 4 neutropenia < 7 days
 - Grade 4 lymphopenia or leukopenia
 - Isolated Grade 4 amylase or lipase abnormalities that are not associated with symptoms or clinical manifestations of pancreatitis. PI and Data Safety and Monitoring Committee (DSMC) should be consulted for Grade 4 amylase or lipase abnormalities.
 - Isolated Grade 4 electrolyte imbalances/abnormalities that are not associated with clinical sequelae and are corrected with supplementation/appropriate management within 72 hours of their onset

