 - Grade 4 drug related endocrinopathy adverse events, such as adrenal insufficiency, ACTH deficiency, hyper- or hypothyroidism, or glucose intolerance, which resolve or are adequately controlled with physiologic hormone replacement (corticosteroids, thyroid hormones) or glucose-controlling agents, respectively, may not require discontinuation.
- Any event that leads to interruption in dosing lasting > 6 weeks (42 days) from the previously required dose requires discontinuation, with the following exceptions:
 - Dosing interruptions to allow for prolonged steroid tapers to manage drug-related adverse events are allowed. Prior to re-initiating treatment in a subject with a dosing interruptions lasting > 6 weeks from the previous dose, the PI and DSMC must be consulted. Tumor assessments should continue as per protocol even if dosing is interrupted. Periodic study visits to assess safety and laboratory studies should also continue every 4 weeks or more frequently if clinically indicated during such dosing interruptions.
 - Dosing interruptions lasting > 6 weeks from the previous dose that occur for non-drug- related reasons may be allowed if approved by the PI and DSMC. Prior to re-initiating treatment in a subject with a dosing interruption lasting > 6 weeks, the PI and DSMC must be consulted. Tumor assessments should continue as per protocol even if dosing is interrupted. Periodic study visits to assess safety and laboratory studies should also continue every 4 weeks or more frequently if clinically indicated during such dosing interrupted.
 - Any adverse event, laboratory abnormality, or intercurrent illness, which in the judgment of the Investigator, presents a substantial clinical risk to the subject with continued nivolumab dosing.
 - If the patient is still receiving clinical benefit, he or she can hold drug for a maximum of 42 days (6 weeks), or 60 days with approval from the DSMC, and subsequently continue therapy following the original treatment schedule.

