4.4 Treatment with ipilimumab and or nivolumab beyond progression

In the event of an initial assessment of PD (based on RECIST Version 1.1), a subject may continue to receive the assigned study treatment as long as none of the criteria listed below are met.

- a. Confirmed PD: a subsequent scan obtained no sooner than 4 weeks from prior scan is suggestive of PD by RECIST 1.1 (see section 6.6), and the patient has clinical decline. NOTE: If PD is confirmed but the patient continues to have clinical benefit (e.g. improvement of symptoms and is tolerating treatment), the patient can continue treatment beyond PD per clinician's discretion.
- b. Meets any of the other investigational product discontinuation criteria (Section 4.3.2)
- c. Clinical symptoms or signs indicating significant PD, for example the benefit-risk ratio of continuing therapy is no longer justified.
- d. Decline in ECOG performance status.
- e. Threat to vital organs/critical anatomical sites (e.g., spinal cord compression) requiring urgent alternative medical intervention, and continuation of study therapy would prevent institution of such intervention.

If the lesions included in the tumor burden subsequently regress to the extent that the criteria for PD are no longer met, then treatment may continue according to the treatment schedule.

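### The Appendix D hepatic note permits delay for combined AST/ALT and bilirubin elevations at which section 4.3.2 requires permanent discontinuation, and no text says which rule prevails

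*Combined protocol and SAP*

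**What the plan says.** Section 4.3.2 lists the grounds for permanent discontinuation. For the liver it states: "Any drug-related liver function test (LFT) abnormality that meets the following criteria require discontinuation". Four criteria follow:

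- "AST or ALT > 5-10 x ULN for > 2 weeks"
- AST or ALT above 10 x ULN
- total bilirubin above 5 x ULN
- "Concurrent AST or ALT > 3 xULN and total bilirubin > 2 x ULN"

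Only the first has a duration attached. The section applies the stop to the drug held responsible, or to both if attribution is not possible.

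Appendix D gives recommended algorithms for suspected nivolumab-related toxicity. The printed note to the hepatic algorithm reads: "I-O therapy may be delayed rather than discontinued if AST/ALT ≤ 8 x ULN or T.bili ≤ 5 x ULN". It mentions neither concurrent elevation nor duration, and does not refer to section 4.3.2.

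Under section 4.3.1, patients who meet the delay criteria for drug-related toxicity "should have both drugs (ipilimumab and nivolumab) delayed until retreatment criteria are met". The delay ends when the toxicity has settled to Grade 1 or less, or to baseline.

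Section 4.3.2 also contains a time limit: "Any event that leads to interruption in dosing lasting > 6 weeks (42 days) from the previously required dose requires discontinuation". It has exceptions, among them: "Dosing interruptions to allow for prolonged steroid tapers to manage drug-related adverse events are allowed". Restarting after such a long interruption requires consultation with the PI and the DSMC.

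**The concern.** Two current parts of the protocol answer the same clinical question differently. Section 4.3.2 makes a combined rise in transaminases and bilirubin a reason to stop for good. The Appendix D note offers delay in place of stopping over limits that take in much of that combination.

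A delay can end in re-treatment. A clinician managing hepatitis from the appendix could wait for the liver tests to settle and then restart a drug that section 4.3.2 says must not be given again. The readable text of section 4.3 does not mention Appendix D, and the note does not send the reader to section 4.3.2, so nothing brings the two rules together at the point of decision.

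The 42-day limit does not close the gap. It applies to long interruptions. For a restart within 42 days no consultation with the PI or DSMC is stated.

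**Working it through.** The plan gives no figure to reproduce. The check is whether any set of liver values meets both rules.

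**Inputs.** Let a be AST or ALT and b total bilirubin, both in multiples of ULN, and let w be the duration in weeks. All abnormalities are taken to be drug-related.

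- Section 4.3.2, stop if: (5 < a ≤ 10 and w > 2), or a > 10, or b > 5, or (a > 3 and b > 2).
- Appendix D note, literal 'or', delay allowed if: a ≤ 8 or b ≤ 5.
- Appendix D note, read as paired limits, delay allowed if: a ≤ 8 and b ≤ 5.

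**Cases.**

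| a | b | w | Section 4.3.2 | Note, literal 'or' | Note, paired limits | Result |
|---|---|---|---|---|---|---|
| 4 | 2.5 | any | stop | delay | delay | conflict on the printed note |
| 6 | 4 | any | stop | delay | delay | conflict |
| 8 | 5 | any | stop | delay | delay | conflict |
| 12 | 1 | any | stop | delay | not allowed | conflict under literal 'or' only |
| 2 | 6 | any | stop | delay | not allowed | conflict under literal 'or' only |
| 6 | 1 | 1 | no stop | delay | delay | none |
| 6 | 1 | 3 | stop | delay | delay | reconcilable: delay first, stop after 2 weeks |

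**Overlap on the printed note.** The concurrent criterion (a > 3 and b > 2) combined with the paired limits (a ≤ 8 and b ≤ 5) gives 3 < a ≤ 8 with 2 < b ≤ 5. Anything allowed under paired limits is also allowed under the literal 'or', so this range conflicts on both readings. The literal reading adds to it, as the cases (12, 1) and (2, 6) show.

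**Sensitivity to the missing flowchart.** The asterisk belongs to a box that is not shown. As context only, the Amendment 4 entry in the summary of changes describes discontinuation starting at AST/ALT above 5 or bilirubin above 3 x ULN. Assume the note is an exception to that box.

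- If either threshold suffices, only the corner 3 < a ≤ 5 with 2 < b ≤ 3 leaves the overlap.
- If both thresholds had to be exceeded, the overlap would be 5 < a ≤ 8 with 3 < b ≤ 5.

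The case (6, 4) conflicts under each of these assumptions.

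**Can delay satisfy section 4.3.2?** For the criterion with a 2-week duration it can: the drug is held and then stopped if the elevation persists. For the concurrent criterion it cannot, because that has no duration and applies as soon as it is met.

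**The case against.** The strongest reply is that the protocol's wording already points to section 4.3.2. That is the section devoted to discontinuation, and it uses mandatory language. Section 4.4 cites it for the discontinuation criteria. Appendix D is headed as recommended, and its note says 'may'. A clinician who follows section 4.3.2 breaches nothing in the appendix. All of this stands, and it lowers the risk. It does not remove the inconsistency, because the note expressly permits what section 4.3.2 rules out and no sentence settles precedence.

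A second reply is that the flowchart may itself carry an instruction for concurrent elevation. That cannot be excluded. The point rests on the printed note, which has none.

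A third is that restarting is not always a breach. Where the toxicity is attributed to one drug, section 4.3.2 requires only that drug to stop, so resuming the other can be compliant. This is correct, and it limits the harm to restarting the drug that should have been stopped.

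A reader might go further and count how many of the four liver criteria are contradicted. The documents do not support a firm count: it depends on whether the printed 'or' is taken literally or as paired limits. A reader might also call the 2-week criterion a direct conflict. The note's silence on duration is better seen as an omitted cross-reference, since both rules can be followed in sequence.

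**Conclusion.** The inconsistency is real and worth correcting. On the printed note it covers at least AST/ALT >3 to 8 with bilirubin >2 to 5 x ULN, on either reading of 'or'. The narrower range of >5 to 8 with >3 to 5 remains under the flowchart assumptions tested. Under the literal 'or' the note also reaches AST/ALT above 10 with low bilirubin, and bilirubin above 5 with low AST/ALT.

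This is a range of laboratory values, not a share of patients. A reader might infer a rate from the Grade 3-4 ALT (8.4%) and AST (5.9%) increases in the pooled melanoma data of section 1.2.4. Those come from a different regimen with ipilimumab 3 mg/kg, and concurrent bilirubin elevation is not reported, so they do not give one.

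A reader might also infer that the design's error rates are affected. They are not: no stated figure depends on this note. Discontinuations before 24 weeks do feed the stopping rules in section 4.5, so the rule a site follows could move that count, but the documents give no basis for saying by how much.

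The conclusion assumes that the abnormality is drug-related and that the unseen flowchart contains no exception for concurrent elevation.

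**What to change.** Add one qualifier to the end of the hepatic note: *provided that no discontinuation criterion in section 4.3.2 is met; section 4.3.2 governs liver-related discontinuation.* By construction this removes every overlap on either reading of 'or'. It keeps delay available where section 4.3.2 allows it, for example AST/ALT 6 x ULN with bilirubin 1 x ULN at day 7. The flowchart should be checked for consistency at the same time.

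Two broader edits are tempting and should be avoided:

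- **Changing 'or' to 'and'.** This would withdraw delay for isolated AST/ALT >8 to 10 x ULN lasting 2 weeks or less. At AST/ALT 9 and bilirubin 1 for one week, no section 4.3.2 criterion is met, yet 9 exceeds the limit of 8.
- **A general sentence that the stricter rule applies.** If the flowchart box does start at AST/ALT above 5 x ULN, this would force an immediate stop where section 4.3.2 waits 2 weeks.

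Neither is needed once the qualifier is in place, and both could cause stops that section 4.3.2 does not require.

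The cost is one footnote clause in an amendment, with the IRB and BMS review that section 11.2 requires. Sample size and data collection do not change.
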